3.4. Efficacy Parameters

3.4.1. Investigator Bruising Severity Scale

3.4.1.1. Investigator Bruising Severity Scale Rating

The Investigator Bruising Severity Scale Rating is directly obtained from the investigator's assessments of each buttock at an evaluation visit.

3.4.1.2. Baseline Investigator Bruising Severity Scale Rating

The Baseline Investigator Bruising Severity Scale Rating is the rating obtained for this item from the investigator's assessments on Day 1.

3.4.1.3. Change from Baseline Investigator Bruising Severity Scale Rating

The change from baseline Investigator Bruising Severity Scale Rating will be the visit rating minus the baseline rating. A negative change in score indicates a reduction in subject bruising severity, while a positive change in score indicates an increase in subject bruising severity.

3.4.2. I-GAIS

3.4.2.1. I-GAIS Rating

The I-GAIS rating is directly obtained from the investigator's assessments of each buttock at an evaluation visit.

3.4.2.2. One-Level I-GAIS Responder

One-level I-GAIS Responder is defined as any subject with an improved (+1, +2 or +3) score on the I-GAIS at an evaluation visit.

3.4.3. I-BIS Rating

The I-BIS rating is directly obtained from the investigator's assessment rating comparing the bruising of the mitigation-treated buttock to the untreated (with mitigation treatment) buttock at an evaluation visit. Note that this assessment cannot be completed in either subjects that do not receive mitigation treatment (Cohort 1) or subjects that receive bilateral mitigation treatment (eg, Cohort 2 - compression garments) since the subjects in those two cohorts do not have a untreated buttock as a comparator.

3.4.4. S-BIS Rating

The S-BIS rating is directly obtained from the subject's assessment rating comparing the bruising of the mitigation-treated buttock to the untreated (with mitigation treatment) buttock. Note that this assessment cannot be completed in either subjects that do not receive mitigation treatment (Cohort 1) or subjects that receive bilateral mitigation treatment (eg, Cohort 2 – compression garments) since the subjects in those two cohorts do not have a untreated buttock as a comparator.

3.4.5. Patient Bothered by Bruising Scale Rating

The Patient Bothered by Bruising Scale rating is directly obtained from the subject's answer to the question "how bothered are you with the appearance of the bruising on your left/right buttock?" for each buttock. To complete this assessment, subjects may use either a mirror or photographs captured by the subject or another person with the subject's imaging device, or images captured by the investigator or designee using the site's digital photography system.

3.5. Safety Parameters

3.5.1. Adverse Events and Treatment-Emergent Adverse Events

Adverse events will be mapped to system organ class and preferred term using the Medical Dictionary for Regulatory Activities (MedDRA). Treatment-emergent adverse events (TEAEs) are any AEs with a start date equal to or after the date of the first injection of QWO (CCH-aaes).

3.5.1.1. Adverse Event Duration

Duration of an AE will be the AE end date minus the AE start date + 1. If AEs are still ongoing at the end of the study or AEs have partial start or stop dates, durations of those AEs are not determined.

3.5.1.2. Intensity of Adverse Events

Intensity (or severity) of AEs will be graded as "mild", "moderate" or "severe". For AEs with missing severity, the most severe assessment will be imputed for analyses, following worst-case principle. If the intensity of an AE changes, then the most severe intensity during the continuous episode will be recorded.

3.5.1.3. Relationship to QWO (CCH-aaes)

The causal relationship with study drug (QWO [CCH-aaes]) will be classified by the investigator and will be reported as follows:

- Not related.
- Unlikely related.
- Possibly related.
- Probably related.

QWO-related adverse events are AEs with the relationship described by the investigator as "probably related" or "possibly related". "Not related" or "unlikely related" causality assessments are considered as not related.

Any missing relationship of an AE to QWO (CCH-aaes) will be considered as related for the analyses, following worst-case principle.

3.5.1.4. Relationship to Mitigation Treatment

The causal relationship with mitigation treatment will be classified by the investigator and will be reported as follows:

• Not related.

- Unlikely related.
- Possibly related.
- Probably related.

Mitigation-related adverse events are AEs with the relationship described by the investigator as "probably related" or "possibly related". "Not related" or "unlikely related" causality assessments are considered as not related.

Any missing relationship of an AE to mitigation treatment will be considered as related for the analyses, following worst-case principle.

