2.4.2. Mitigation Treatments

Mitigation treatments will be provided locally by each investigator/subject.

At the investigator's discretion and with consent of the subject, mitigation treatments provided after the first treatment session of QWO (CCH-aaes), can be administered after the second and third QWO (CCH-aaes) treatment sessions. Mitigation treatments administered after each treatment session with QWO (CCH-aaes) may be recorded as concomitant medications.

Cohort 1 will serve as a control and no mitigation treatment will be administered.

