2.11. Adverse Events

Adverse Events (AEs), including both observed or volunteered problems, complaints, signs or symptoms must be recorded, regardless of whether associated with the use of study treatment. Study treatment includes QWO (CCH-aaes) and mitigation treatments.

The following information will be collected for all AEs:

- Verbatim description
- Injection Site Reaction (Yes/No)
- Date of Onset

- Date of Resolution/or Ongoing
- Severity (Mild, Moderate, Severe)
- Relationship to QWO (CCH-aaes) (Not Related, Unlikely Related, Possibly Related, Probably Related)
- Action taken with QWO (CCH-aaes) (None, Interrupted, Withdrawn)
- Relationship to Mitigation Treatment (Not Related, Unlikely Related, Possibly Related, Probably Related)
- Action taken with Mitigation Treatment (None, Interrupted, Withdrawn)
- Outcome (Recovered/Resolved, Recovered/Resolved w/Sequelae, Recovering/ Resolving, Not Recovered/Not Resolved, Fatal, Unknown)
- Whether or not a concomitant medication or procedure was required
- Classified as a serious adverse event (SAE) or not
- SAE Code (Death, Life-threatening, Inpatient or prolonged hospitalization, Persistent or significant disability/incapacity, Congenital anomaly or birth defect, Other medically important event)

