3.3.3. Cohorts

The cohorts will be structured as described in Table 1, and will be summarized by the mitigation treatment used:

- Cohort 1: No mitigation treatment (control)
- Cohort 2: Compression garments
- Cohort 3: Instant cold packs
- Cohort 4: Arnica gel patches (OcuMend)
- Cohort 5: INhance post-injection serum with TriHex technology
- Cohort 6: Pulse Dye Laser (PDL) treatment

Once subjects are assigned to a particular cohort using the site-specific Mitigation Treatment Assignment Table, the cohort assignments will remain regardless of the actual treatment received. Subjects who receive a different mitigation treatment at any time from the mitigation treatment to which they were assigned will be reported as a protocol deviation.

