5.7.5. Exploratory Endpoints –

5.8. Safety Evaluation

5.8.1. Adverse Events

The following listings will be provided based on all AEs:

- Listing of deaths.
- Listing of non-fatal SAEs.
- Listing of non-serious AEs leading to discontinuation from study.

Listing of non-serious AEs leading to interruption or discontinuation of either QWO (CCH-aaes) or mitigation treatment. The following summary tables of AEs will be presented by cohort:

- TEAEs
 - Overall summary
 - By preferred term
 - By preferred term and severity
 - By frequency of SAEs
 - By frequency of most common non-SAE
- QWO-related AEs
 - Overall summary
 - By preferred term
 - By preferred term and severity
- Mitigation-related AEs
 - Overall summary
 - By preferred term
 - By preferred term and severity

The overall summary will consist of the following items:

- Total number of AEs
 - All AEs
 - Mild AEs
 - Moderate AEs
 - Severe AEs
 - Related to QWO (CCH-aaes) Only (TEAEs overall summary only)
 - Related to Mitigation Only (TEAEs overall summary only)
 - Related to both QWO (CCH-aaes) and Mitigation (TEAEs overall summary only)
- Total number of subjects with
 - At least 1 AE

- At least 1 SAE
- At least 1 severe AE
- No severe AEs but at least 1 moderate AE
- No severe/moderate AEs but at least 1 mild AE
- At least 1 AE leading to discontinuation from study
- At least 1 AE leading to interruption or discontinuation of QWO (CCH-aaes) only (TEAE overall summary only)
- At least 1 AE leading to interruption or discontinuation of Mitigation Treatment only (TEAE overall summary only)
- At least 1 AE leading to interruption or discontinuation of both QWO (CCH-aaes) and Mitigation Treatment (TEAE overall summary only)
- Total number of subjects who died (TEAEs overall summary only)

Percentages for the total number of mild, moderate, and severe AEs will be based on the total number of all AEs in the cohort.

The by frequency summaries will also include the total number of occurrences the AE preferred term was reported as well the number of subjects with at least 1 report of the AE. Most common non-SAEs are any preferred term AE that at least 5% of the subjects in any cohort report at least once.

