6.2. Safety Variables

6.2.1. Adverse Events

Adverse events will be organized in 2 different ways: by event and by subject. The by event dataset will include all the characteristics of the event obtained on the eCRF plus the derived variables presented in Table 12. A second by event dataset will be created for the AE duration analysis. This duration dataset will contain only the subject number, treatment session, body system classification, preferred term, and duration.

Variable	Values/Definition
Treatment-Emergent	AE with a start date after the first dose of study medication
QWO-Related	If relationship to QWO (CCH-aaes) is reported as possible, probable or missing; 'unlikely related' AE will be classified as not a drug-related AE.
Mitigation-Related	If relationship to study mitigation only is reported as possible, probable or missing; 'unlikely related' AE will be classified as not a mitigation-related AE.
Onset Day	AE Start Date - Date of First Injection + 1
Duration	AE Stop Date - AE Start Date + 1

Table 12:Adverse Event Variables by Event

AE=Adverse event

The by-subject dataset will summarize all the AE events for a subject and will include the variables presented in Table 13. The same variables will be computed for TEAEs and treatment-related AEs.

Table 13:Adverse Event Variables by Subject

Variable	Values/Definition
Total AEs	Sum of number of AEs the subject reported
Total Mild AEs	Sum of number of mild AEs the subject reported
Total Moderate AEs	Sum of number of moderate AEs the subject reported
Total Severe AEs	Sum of number of severe AEs the subject reported
Had AE	Flag (Y/N) to indicate subject had at least 1 AE
Had Severe AE	Flag (Y/N) to indicate subject had at least 1 AE of moderate or severe severity
Had SAE	Flag (Y/N) to indicate subject had at least 1 serious AE

Variable	Values/Definition
Had AE Leading to Discontinuation	Flag (Y/N) to indicate subject had at least 1 AE that led to discontinuation from the study
Had AE Leading to Interruption/Withdrawal of QWO (CCH-aaes)	Flag (Y/N) to indicate subject had at least 1 AE that led to interruption/withdrawal of QWO (CCH-aaes)
Had AE Leading to Interruption/Withdrawal of Mitigation	Flag (Y/N) to indicate subject had at least 1 AE that led to interruption/withdrawal of Mitigation treatment

 Table 13:
 Adverse Event Variables by Subject (Continued)

AE=Adverse event; SAE=Serious adverse event; Y/N=Yes/No

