[1] Results as reported using the Patient Bothered by Bruising Scale.

[2] Percentages are based on number of subjects with non-missing assessments at an evaluation visit.

[3] Based on results recorded at the Day 22 visit, before injection.

Note: By design, Cohort 1 did not receive any mitigation treatment. For Cohort 2, mitigation treatment was administered to both left and right buttocks. For Cohorts 3-6, mitigation treatment was administered to right buttock only.

Evaluable Population includes all enrolled subjects who received at least 1 injection of QWO (CCH-aaes) with or without mitigation treatment and have at least one bruising assessment after the first dose of QWO (CCH-aaes).

Datasets (extraction): status(ddmmmyyyy), Source: ...\xxxxxx.sas

Programming note: please include columns for cohorts 1-2 on page 1, columns for cohorts 3-4 on page 2, and columns for cohorts 5-6 on page 3. Cohort column headers should read: "Cohort 1 No Mitigation", "Cohort 2 Compression", "Cohort 3 Cold Packs", "Cohort 4 Arnica Patches", "Cohort 5 INhance Serum", "Cohort 6 PDL Treatment".

Datasets (extraction): status(ddmmmyyyy), Source: ...\xxxxxx.sas

ddmmmmyyyy:HHMM

Programming note: please include columns for cohorts 1-2 on page 1, columns for cohorts 3-4 on page 2, and columns for cohorts 5-6 on page 3. Cohort column headers should read: "Cohort 1 No Mitigation", "Cohort 2 Compression", "Cohort 3 Cold Packs", "Cohort 4 Arnica Patches", "Cohort 5 INhance Serum", "Cohort 6 PDL Treatment".

			Table 14.3.1.	.1		
Overall	Summary	of	Ireatment-Eme	ergent	Adverse	Events
		S	fety Populat	ion		

Parameter	Statistic	Cohort 1 No Mitigation (N=xxx)	Cohort 2 Compression (N=xxx)	 Cohort 6 PDL Treatment (N=xxx)
Fotal Number of TEAEs Reported [1]	n	XX	Xx	 XX
Total Number of Mild TEAEs [1]	n (%)	xx (xx.x)	xx (xx.x)	 xx (xx.x)
Total Number of Moderate TEAEs [1]	n (%)	xx (xx.x)	xx (xx.x)	 xx (xx.x)
Total Number of Severe TEAEs [1]	n (%)	xx (xx.x)	xx (xx.x)	 xx (xx.x)
Total Number of TEAEs related to QWO only [2]	n (%)	xx (xx.x)	xx (xx.x)	 xx (xx.x)
Total Number of TEAEs related to Mitigation only [2]	n (%)	xx (xx.x)	xx (xx.x)	 xx (xx.x)
Total Number of TEAEs related to both QWO and Mitigation [2]	n (%)	xx (xx.x)	xx (xx.x)	 xx (xx.x)
Number of Subjects Reporting TEAEs:				
At least one TEAE	n (%)	xx (xx.x)	xx (xx.x)	 XX (XX.X)
At least one Serious TEAE	n (%)	xx (xx.x)	xx (xx.x)	 XX (XX.X)
At least one Severe TEAE	n (%)	xx (xx.x)	xx (xx.x)	 XX (XX.X)

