No Severe TEAE, but at least one Moderate TEAE	n (%)	xx (xx.x)	xx (xx.x)	 XX (XX.X)
No Severe/Moderate TEAEs, but at least one Mild TEAE	n (%)	xx (xx.x)	xx (xx.x)	 xx (xx.x)
At least one TEAE Leading to Withdrawal from Study	n (%)	xx (xx.x)	xx (xx.x)	 xx (xx.x)
At least one TEAE Leading to Interruption/Discontinuation of OWO (CCH-aaes) only	n (%)	xx (xx.x)	xx (xx.x)	 xx (xx.x)
At least one TEAE Leading Interruption/Discontinuation of Mitigation Treatment only	n (%)	xx (xx.x)	xx (xx.x)	 xx (xx.x)
At least one TEAE Leading to Interruption/Discontinuation of both QWO (CCH-aaes) and Mitigation Treatment	n (%)	xx (xx.x)	xx (xx.x)	 xx (xx.x)
Number of Subjects with TEAEs Resulting in Death	n	XX	XX	 XX

[1] Treatment emergent adverse events (TEAEs) are adverse events with a start date after the first dose of QWO (CCH-aaes). Total number of adverse events reported includes the same adverse event occurring multiple times for a subject being counted at each occurrence. Percentages were based on the overall total number of all adverse events within the cohort.

[2] Treatment emergent adverse events (TEAEs) reported as having possibly or probably related to either QWO, or mitigation treatment, or both. Missing relationships were considered as related.

Note: Safety Population includes all enrolled subjects who received at least 1 injection of QWO (CCH-aaes) with or without mitigation treatment.

Datasets (extraction): status(ddmmmyyyy), Source: ...\xxxxxx.sas

Programming note: please include columns for cohorts 1-3 on page 1, and columns for cohorts 4-6 and Overall on page 2 if it is impossible to put all columns in one page. Cohort column headers should read: "Cohort 1 No Mitigation", "Cohort 2 Compression", "Cohort 3 Cold Packs", "Cohort 4 Arnica Patches", "Cohort 5 INhance Serum", "Cohort 6 PDL Treatment".

Table 14.3.1.2 Overall Summary of QWO-Related Adverse Events Safety Population

Datasets (extraction): status(ddmmmyyyy), Source: ...\xxxxxx.sas ddmmmmyyyy:HHMM

Programming note: Use same format as Table 14.3.1.1 with QWO- Related Adverse Events only. Replace TEAE with QWO-Related AEs. Do not include rows "Related to xxx" and "At least 1 AE leading to interruption or discontinuation of xxx".

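### A missing relationship to mitigation is imputed as related without regard to exposure, so a blank in the no-mitigation control cohort would be reported as a mitigation-related adverse event

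*SAP*

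**What the plan says.** The rule in SAP 3.5.1.4 (Relationship to Mitigation Treatment) is: "Any missing relationship of an AE to mitigation treatment will be considered as related for the analyses, following worst-case principle". SAP 6.2.1, Table 12, carries it into the derived flag for mitigation-related events: "If relationship to study mitigation only is reported as possible, probable or missing". Neither place sets a condition on cohort or on receipt of mitigation.

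On exposure, SAP 2.4.2 says: "Cohort 1 will serve as a control and no mitigation treatment will be administered".

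On data capture, SAP 2.11 includes relationship to mitigation among the items collected for every AE. It gives four response options, from not related to probably related, and none for not applicable.

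On output, SAP 5.8.1 says "The following summary tables of AEs will be presented by cohort", and the list that follows includes mitigation-related AEs. Table 14.3.1.1 has a Cohort 1 column and separate rows for TEAEs related to QWO only, to mitigation only, and to both. Its footnote adds: "Missing relationships were considered as related". The programming notes build Table 14.3.1.3 from Table 14.3.1.1, Table 14.3.2.3 from Table 14.3.2.1, and Table 14.3.3.3 from Table 14.3.3.1. All three source shells have a Cohort 1 column.

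**The concern.** Worst-case imputation of causality is conservative where the subject was exposed, because a blank might hide a true relationship. Where there was no exposure, there is nothing to be conservative about, and the rule creates an attribution that cannot be true.

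The SAP handles the same issue elsewhere. It leaves Cohort 1 out of the mitigation exposure summaries (SAP 5.7.1.2, Table 14.2.2) and out of the I-BIS and S-BIS tables. It makes no such provision for the mitigation-related AE tables.

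Safety of QWO with mitigation treatment is a secondary objective, and these tables report the attribution side of it. With about 8 subjects per cohort, one false entry in the control column is conspicuous and would have to be explained in the study report.

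**Working it through.** **Tracing the rule for one event.** Take a Cohort 1 subject with bruising assessed as probably related to QWO and the mitigation field blank.

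1. SAP 3.5.1.4 and Table 12: blank becomes mitigation-related, since no exposure condition stops it.
2. Tables 14.3.1.3, 14.3.2.3 and 14.3.3.3: she is counted in the Cohort 1 column.
3. Table 14.3.1.1: the event leaves the QWO-only row and enters the both row. Had it been unrelated to QWO, it would enter the mitigation-only row.
4. Unchanged: total TEAEs, and the QWO-related tables (14.3.1.2, 14.3.2.2, 14.3.3.2), because the QWO flag is derived separately (SAP 3.5.1.3, Table 12).

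**Inputs for the size.**
- Cohort size: about 8 in each of 6 cohorts (SAP 8). Check: 6 × 8 = 48, the stated total.
- Bruising incidence: 84% in Phase 3 (Protocol 2.1), used only as an illustration.
- m, the chance that a Cohort 1 subject with a bruising AE has the mitigation field blank. The documents give no value, so a range is assumed.

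**One affected subject.** 1/8 = 12.5 percentage points.

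**Chance of at least one affected control subject.** With subjects independent, this is 1 − (1 − 0.84m)^8. The expected number is 8 × 0.84m.

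| Assumed m | 0.84m | Expected subjects of 8 | Chance of at least one |
|---|---|---|---|
| 1% | 0.0084 | 0.07 | 6.5% |
| 2% | 0.0168 | 0.13 | 12.7% |
| 5% | 0.042 | 0.34 | 29.1% |
| 10% | 0.084 | 0.67 | 50.4% |
| 25% | 0.21 | 1.68 | 84.8% |
| 100% (ceiling) | 0.84 | 6.72 | nearly 100% |

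The calculation counts bruising AEs only, so blanks on other AEs would add to it. If blanks cluster by site rather than falling independently, the chance of at least one is lower, but more subjects are affected when it happens.

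**With the imputation limited to subjects who received mitigation.** Imputation adds 0 of 8 in an unexposed Cohort 1, whatever m is.

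**The case against.** The artefact needs a blank, and the documents give some reason to expect few. The field is collected for all AEs (SAP 2.11), the investigator is to classify it (SAP 3.5.1.4), and Protocol 10.2.2 defines *Not related* in terms that suit a subject given no mitigation. The shell of Listing 16.2.7.1 shows Cohort 1 example rows filled with *Not Related* for mitigation. The eCRF itself is not available. The SAP's option lists may not transcribe it exactly: for action taken, SAP 2.11 has None where SAP 3.5.1.5 has Not changed. All of this stands against any claim about how often blanks will occur. It does not cure the rule, because a listing shell is sample text and no passage tells sites what to enter for an unexposed subject.

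A reader might go further in three ways that the documents do not support.

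- *Blank is the natural entry for Cohort 1, so about 7 of 8 controls will be counted.* No text says so, and the points above lean the other way. The 6.72 is the ceiling if every such field is blank, not a forecast.
- *The control reference for mitigation-related AEs is lost.* A cohort given no mitigation has zero by definition, not an estimated background rate. The TEAE counts by cohort remain intact.
- *QWO reactions are generally misattributed.* Only the relationship rows of Table 14.3.1.1 and the three mitigation-related tables shift. Listing 16.2.7.1 shows both relationships for each AE, so an odd entry can be traced.

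Broader remedies also have drawbacks. Setting every AE that starts before first mitigation to not applicable would overwrite recorded judgements. PDL is applied to bruising already observed, up to Day 7 (SAP 2.4.2.5), and a worsening stays within the same continuous episode (SAP 3.5.1.2). A bruise judged related to PDL could therefore carry an earlier onset date. Same-day order cannot be recovered either, since SAP 3.3.2 records dates and not times. Dropping the Cohort 1 column could hide events in a control subject given mitigation in error, who stays in her assigned cohort under SAP 3.3.3.

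**Conclusion.** The point holds as a defect in a stated rule. As written, any blank relationship to mitigation in Cohort 1 becomes a mitigation-related AE in Tables 14.3.1.3, 14.3.2.3 and 14.3.3.3, and shifts the attribution rows of Table 14.3.1.1. One such subject shows as 12.5%.

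How likely this is depends on a missing rate that the documents do not give. At assumed rates of 1%, 5% and 10%, the chance of at least one affected control subject is about 6.5%, 29% and 50%. Those figures rest on the 84% incidence carrying over from Phase 3, on exactly 8 controls, and on independence between subjects.

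The effect is confined to descriptive attribution tables. The primary bruising endpoint is untouched.

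**What to change.** - **SAP 3.5.1.4 and Table 12:** apply the missing-equals-related rule only to subjects with at least one mitigation treatment recorded on the Study Mitigation Treatment eCRF page. For subjects with none, treat a missing relationship as not applicable and do not count it as mitigation-related.
- **Non-missing values:** leave every recorded investigator assessment unchanged, in all cohorts.
- **Tables 14.3.1.1, 14.3.1.3, 14.3.2.3 and 14.3.3.3:** keep the Cohort 1 column, with a footnote that no mitigation was planned for that cohort, and align the footnote on missing relationships with the amended rule. Any mitigation given in error then stays visible.

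A blank on an AE that starts before mitigation in Cohorts 2 to 6 would still count as related. That is conservative, and dates alone cannot refine it reliably.

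The cost is one sentence, one programming condition on data already collected (SAP 3.3.2), and footnote edits to four shells. No new data are needed.
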